## **9.9 LIMITATIONS OF THE RESEARCH METHODS**

There are several methodological challenges when conducting epidemiologic studies to evaluate the association between glucose lowering drugs and outcomes of interest among patients with diabetes. These challenges include, but are not limited to, changes in treatment in response to advancing diabetes or due to adverse effects of specific drugs and time-varying

risk of an outcome [[P12-13528](#), [P14-17457](#), [R14-4378](#)]. Other limitations of the study are listed below.

### **9.9.1 Data source**

The source claims data include limitations with respect to certainty of the capture of exposure, covariates, and outcomes. As a comprehensive insurance database, essentially all billable medical services will result in claims for reimbursement, so that the certainty of capture is tied to likelihood of a claim being submitted to the insurer.

Although duration of diabetes may represent a risk factor for the study outcome, this covariate will be incompletely captured since the patient history in the dataset is relatively short (at least 12 months, and an average of approximately 2 years), and a first claim within the database may not represent diabetes onset since the condition can be latent for some time and is typically not treated with hypoglycaemic medications at its diagnosis.

New initiators are operationally defined as patients with no use in the prior 6 months. This does not ensure, however, that patients have never used the drug of interest; the possibility remains that these patients were treated at some prior time point before they enrolled in their insurance plan.

There is potential for misclassification of dose based on healthcare utilization data, but the “days supply” field is expected to be fairly accurate. Similar concern may be present for exposure classification as well, but we expect the drug codes utilized in the data sources will appropriately represent the drug that is being classified.

Medication use in administrative healthcare databases is restricted to prescription drug medication. Consequently, the use of over-the counter (OTC) medications (e.g., OTC aspirin) is not captured. Additionally, the indication of a claim for prescription medications does not confirm whether the medication was actually taken by the patient or taken as prescribed.

It is estimated that two databases (MarketScan and Optum CDM) have about 10-15% overlap and it is not possible to identify duplicates and remove them between the two databases because patients are de-identified. It is not expected that this overlap impacts the results of this study because it will be much smaller in the study population. Furthermore, there is a sensitivity analysis to consider several scenarios of overlap in patients between the MarketScan and Optum (e.g., 0%, 10%, 20%, etc.), and 95% CIs of primary outcome will be adjusted accordingly.

Given that MarketScan and Optum CDM are claims databases, clinical laboratory data is only available for a small portion of enrollees (approximately 40-50% in Optum CDM and about 5% in [REDACTED] MarketScan).

## **9.9.2 Confounding**

A strength of this active-comparator new-user (rather than non-user) design is that it mitigates much of the confounding bias that can be prominent in comparative observational studies. Although use of propensity scores will facilitate the control of measured confounders, unmeasured and unidentified confounders could still introduce bias if they are differentially distributed among the exposed and comparator groups and are related to the outcome. As an example, use of over-the-counter medications will remain unmeasured in this study.

Confounding by indication or severity, also known as channelling bias, is a common bias in pharmacoepidemiology. Patients starting treatment with a newly marketed drug might have more severe disease than patients not taking the medication either because of self-selection or because of physician preference. They may also have a less severe form of the disease if physicians prefer to test new drugs with a less familiar safety profile in less severely affected patients. New medications may also be prescribed differentially by physicians who are “early adopters” of new technologies and who systematically treat more severely affected patients with the new medications. In previous empagliflozin safety studies, DPP-4 inhibitors were selected as the comparator group because these group of medications (relative to other oral hypoglycemic agents such as metformin and sulfonylureas) were recently introduced in the market. Therefore, using them as comparators reduces the risk of this type of bias. However, in this study, because of the existing association between DPP4 initiators and GLP1 agonists and study outcome (acute pancreatitis), these medications were not selected as comparators. Because of the possibility of channeling bias, the remaining oral hypoglycemic agents (metformin, SU, TZD) were not appropriate for a new user design that utilized a combined comparison group. A prevalent new user design was considered for this study, but because the long-term history of therapies for prevalent users is not typically available in the US claims databases, it was deemed more appropriate to use the active comparator new user design based on treatment lines as mentioned in [section 9.3.1](#).

Study participants in the empagliflozin group will be 1:1 matched with comparators to account for confounders. After PS matching, study participants will be matched based on the calendar quarter year of the cohort entry to help minimize residual confounding.

Although we will try to measure and include all available confounders in the PS models, some important variables e.g. alcohol abuse or smoking which are correlated with the outcome are not available for all study participants. Furthermore, study participants in the comparator groups are probably more prone to have lower socioeconomic status which is a potential for channelling bias that is not easy to detect in our study. These patients may also have different background risk for alcohol use and smoking.

Some of the outcome risk factors, e.g. infection, are only captured via hospital admission claims. Therefore, infections not resulting in hospitalization cannot be captured in this study and this increases the risk of residual confounding.

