### **9.3.2      Outcomes**

#### **9.3.2.1      Primary outcomes**

In this study we will use a modified version of an algorithm developed and validated in the [REDACTED] with a sensitivity of 89.8% and a specificity of 79.4% [[R20-3555](#), [R20-3554](#)]. In the original algorithm, only the Logical Observation Identifiers Names and Codes (LOINC) were used for the lipase measurement but since these codes are only available for a subset of patients in Marketscan and Optum databases, to accommodate database needs, the equivalent Current Procedural Terminology (CPT) codes were added to the algorithm. This modified algorithm is:

- The presence of an acute pancreatitis diagnosis from any of the inpatient (not restricted to the primary diagnosis), outpatient, or emergency contacts diagnoses (ICD-9-CM 577.0 or ICD-10-CM K85)  
AND
- A lipase measure within +/- 7 days of the acute pancreatitis diagnosis (using LOINC code of 3040-3 and 2572-6 or CPT code of 83690 for lipase)  
AND
- An abdominal ultrasound (using CPT codes of 76700 and 76705) within +/- 7 days of the acute pancreatitis diagnosis

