### **9.3.3 Covariates**

Several baseline patient characteristics will be captured in the 6 months prior to the index date. Some of these covariates will be included as covariates in the propensity scores (PS) model.

- Demographics
- Comorbidity indexes: Elixhauser comorbidity index [[R14-4775](#)], Charlson comorbidity index
- Diabetes specific complications
- Comorbidities (e.g. CVD [[R21-0209](#)])
- Prior/concomitant use of other oral glucose lowering drugs
- Prior/concomitant use of other drug(s) associated with acute pancreatitis [[P08-00872](#)]:
  - $\alpha$ -methyldopa, azodisalicylate, bezafibrate, cannabis, carbimazole, codeine, cytosine, arabinoside, dapsone, enalapril, furosemide, isoniazid, mesalamine, metronidazole, pentamidine, pravastatin, procainamide, pyritonol, simvastatin, stibogluconate, sulfamethoxazole, sulinda, tetracycline, valproic acid, all trans-retinoic acid, amiodarone, azathioprine, clomiphene, dexamethasone, ifosfamide, lamivudine, losartan, lynesterol/methoxyethinylestradiol, Mercaptopurine, meglumine, methimazole, nelfinavir, norethindronate/mestranol, omeprazole, premarin, sulfamethazole, trimethoprim-sulfamethazole, acetaminophen, chlorthiazide, clozapine, didanosine, erythromycin, estrogen, L-asparaginase, pegasparagase, propofol, tamoxifen, azathioprine, sulfonamides, tetracyclines, alpha-methyldopa
- Prior/concomitant use of other medications (e.g. cardiovascular medications, full list is added in [annex 5](#))
- Other acute pancreatitis risk factors e.g. abdominal surgery, alcoholism and alcohol abuse, cystic fibrosis, gallstones and other gallbladder and biliary tract disorders, hyperparathyroidism, infection, injury to the abdomen, and lupus
- Specific lab test results (when available, see below and SEAP)
- Coronavirus (COVID-19) infection (this is applicable only to patients who have 2020 data) during the baseline period and follow up

Given the nature of the databases, it will not be possible to include exposure to over-the-counter medications as a covariate in the analysis.

The list of covariates is provided in Appendix 5 and all practical definitions and codes can be found in the statistical epidemiological analysis plan (SEAP).

Laboratory test results in a subset of patients:

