## **9.4 DATA SOURCES**

Two large US claims databases (Truven Marketscan Commercial Claims and Encounters (CCAE), Truven Marketscan Medicare Supplemental (MDCR), and Optum Clininformatics® Data Mart [CDM]) will be used in this study. Meta-analysis of the 2 databases might be used, when appropriate, to achieve the required study size.

Main data elements from each database that will be used in this analysis include: 1) enrolment records, 2) pharmacy dispensing claims (dispensing date, National Drug Code [NDC] to determine product prescribed, quantity, and days of supply, and 3) medical claims (service date, diagnosis codes [ICD-9-CM, ICD-10-CM], procedure codes [Current Procedural Terminology (CPT)-4, ICD-9 Procedure Coding System (PCS), ICD-10-PCS], and laboratory test results (when available).

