ANNEX 3. STUDY COVARIATES

N	Category	Variables	Definition
1	Demographics	Age	
 - By year - By category (18-54, 55-64, 65-74, 75+)
		Gender	
 - Male, Female
		Smoking	
All codes could be found in the following excel file:
  
1245-0201%20codes%20part%201_03022

		Alcohol abuse or dependence	
		Drug abuse or dependence	
		Overweight	
		Obesity	
		Calendar quarter of cohort entry	
2	Comorbidity indexes	Elixhauser comorbidity index	
 - R14-4775
		Charlson comorbidity index	
3	Diabetes specific complications	Diabetes retinal problems	
Diabetic retinopathy, diabetes with other ophthalmic manifestations, Retinal detachment, vitreous hemorrhage, vitrectomy, retinal laser coagulation therapy. Codes presented in the following excel file:
  
1245-0201%20codes%20part%201_03022

		Diabetic neuropathy	
		Diabetic nephropathy	
		Hypoglycaemia	
		Hyperglycaemia	
		Disorders of fluid electrolyte and acid-base balance	
		Diabetic ketoacidosis	
		Hyperosmolar hyperglycemic nonketotic syndrome (HONK)	
		Diabetes with peripheral circulatory disorders	
		Diabetic foot	
		Gangrene	
		Lower extremity amputation (lower extremity amputation diagnosis code, lower extremity amputation procedure code (ICD), lower extremity amputation procedure code (CPT).)	
		Osteomyelitis	
		Skin infections	
		Erectile dysfunction	
		Diabetes with unspecified complication	
		Diabetes mellitus without mention of complications	

BOEHRINGER INGELHEIM Group of Companies
Statistical and Epidemiological Analysis Plan (SEAP) for Non-Interventional Studies (NIS)

c37922104-02

Page 23 of 27

Proprietary confidential information © 2022 Boehringer Ingelheim International GmbH or one or more of its affiliated companies

4	General medical history	Hypertension	Codes presented in the following excel file:  1245-0201%20codes%20part%202_03022
		Hyperlipidaemia	
		Myocardial infarction (Acute MI and old MI)	
		Angina (ACS/unstable angina, stable angina)	
		Coronary atherosclerosis and other forms of chronic ischemic heart disease	
		Cardiac procedures (Previous cardiac procedure (CABG or PTCA or Stent))	
		Ischemic stroke (w and w/o mention of cerebral infarction)	
		Hemorrhagic stroke	
		TIA	
		Cerebrovascular disease (Other cerebrovascular disease, late effects of cerebrovascular disease, Cerebrovascular procedure)	
		Heart failure (CHF)	
		Peripheral Vascular disease or PVD surgery	

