		
 • Antiepileptics • Antiinflammatory and antirheumatic products • Antineoplastic agents • Antipsoriatics • Antithrombotic agents • Beta-blocking agents • Calcium channel blockers • Diuretics • Drugs for acid-related disorders • Drugs for obstructive airway diseases • Immunosuppressants • Lipid-modifying agents • Opioids • Psycholeptics • Psychostimulants, agents used for ADHD, and nootropics 	
9	History of acute pancreatitis risk factors	
 • Abdominal surgery • Alcoholism • Cystic fibrosis • Gallstones and other gallbladder and biliary tract disorders • High calcium levels in the blood (hypercalcemia) • Hyperparathyroidism • Hypertriglyceridemia • Infection • Injury to the abdomen • Lupus • Liver disease • Pancreatic disease 	
Codes are listed in the following excel file:
  
1245-0201%20Code s%20part%204%20-%

10	Lab test results (when available)	
 • amylase (U/L); • lipase (U/L); • white cell count (G/L); • red cell count (T/L); • haemoglobin (g/L); • haematocrit (%); • thrombocyte (G/L); • C-reactive protein (mg/L); • creatinine (μmol/L), 	

BOEHRINGER INGELHEIM Group of Companies
Statistical and Epidemiological Analysis Plan (SEAP) for Non-Interventional Studies (NIS)

c37922104-02

Page 26 of 27

Proprietary confidential information © 2022 Boehringer Ingelheim International GmbH or one or more of its affiliated companies

		
carbamid (mmol/L); serum bilirubin (μmol/L);
 
• GGT (mmol/L);• GOT (mmol/L);• GPT (mmol/L);• ALP (mmol/L);• uric acid (mmol/L);• cholesterol (HDL, LDL) (mmol/L); triglycerides (mmol/L);• serum protein (g/L);• albumin (g/L),• C-peptide (pmol/L);• HgbA1C (%);• OGTT test glucose (mmol/L) and insulin level (pmol/L) at 0, 60 and 120min [add reference].• HbA1c (%)• LDL level (mg/dl)• HDL level (mg/dl)• Total cholesterol (mg/dl)• Triglyceride level (mg/dl)• Creatinine (mg/dl)• BUN (mg/dl)• BNP• NT-proBNP• Lipase	
11	Procedures	
• Abdominal ultrasound	

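### The protocol expects lower socioeconomic status in the comparator groups, but the visible candidate covariate list holds no baseline health-care-use counts, which the claims in hand could supply

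*Protocol*

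**What the plan says.** Protocol section 9.9.2 predicts an imbalance: "study participants in the comparator groups are probably more prone to have lower socioeconomic status which is a potential for channelling bias". It calls this hard to detect in the study and adds: "These patients may also have different background risk for alcohol use and smoking". The same section gives the intent for adjustment: "we will try to measure and include all available confounders in the PS models".

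Section 9.3.3 lists the candidate covariates by category and leaves the final choice open: "Some of these covariates will be included as covariates in the propensity scores (PS) model". SAP Annex 3 spells the list out. Its demographics block holds age, gender, smoking, alcohol and drug abuse, overweight, obesity and "Calendar quarter of cohort entry". Its other blocks are comorbidity indexes, diabetes complications, medical history, insulin and other glucose-lowering drugs, drugs linked to pancreatitis, other drug classes, pancreatitis risk factors and laboratory results. The procedures block has one entry, "Abdominal ultrasound".

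Section 9.4 names the data elements that will be used, among them "enrolment records, 2) pharmacy dispensing claims", followed by medical claims with service dates, diagnoses and procedures.

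**The concern.** The plan names a likely source of channelling and says it will try to adjust for every available confounder. It then lists no measure of how much care a patient used before the index date. Counts of admissions, visits and distinct drugs are common partial proxies for health status, access to care and care-seeking, and they can be derived from data the study already holds.

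The direct measures of the suspected pathway are present but weak by the protocol's own account. Section 9.9.2 says alcohol abuse and smoking are not available for all participants. Section 9.9.3 says alcohol use and obesity are under-reported in claims, and that smoking and alcohol use could not be measured properly.

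What is at stake is the HR set against the 1.5 bound in section 9.5. If lower socioeconomic status among SU users raised their pancreatitis rate, the HR would be pulled down. In a safety study that is the anti-conservative direction.

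A secondary point concerns detection. The outcome algorithm requires "A lipase measure within +/- 7 days of the acute pancreatitis diagnosis" and an abdominal ultrasound in the same window, so case capture may depend partly on intensity of care. The direction of any resulting bias is unknown.

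**Working it through.** **1. Is any health-care-use count listed?** Going through every category in protocol 9.3.3 and every block of SAP Annex 3:

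| Measure | Listed? |
|---|---|
| Hospital admissions, number | No |
| Emergency visits, number | No |
| Outpatient visits, number | No |
| Distinct drugs dispensed, number | No |
| Insurance or source-file type | No |
| Smoking, alcohol abuse, obesity (codes) | Yes, recorded incompletely per 9.9.2 and 9.9.3 |
| Charlson and Elixhauser indexes, drug classes | Yes, reflect care use only indirectly |

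**2. Could the counts be built?** Yes. Section 9.4 provides medical claims with service dates and pharmacy dispensings with product codes, and a 6-month look-back is already required of every patient. Insurance type is less clear. MarketScan consists of a commercial file (CCAE) and a Medicare Supplemental file (MDCR), but no plan-type field is named, and no such split is described for Optum.

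**3. The plan's study-size figure, needed for the event count.** Inputs from section 9.5: both rates 0.0022, ratio bound R = 1.5, one-sided alpha 0.05, power 0.80, 1:1 allocation. The Farrington-Manning constrained rates are 0.001760 and 0.002640.

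- n = (1.645·√v0 + 0.842·√v1)² / (0.0022 − 1.5 × 0.0022)²
- v0 = 0.002640(1 − 0.002640) + 1.5² × 0.001760(1 − 0.001760) = 0.006585
- v1 = (1 + 1.5²) × 0.0022 × 0.9978 = 0.007134
- n = 34,585.4 per group, as stated in Table 1

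Expected events with one year each: 2 × 34,585.4 × 0.0022 = 152.2. The approximate standard error of the log HR is 2/√152.2 = 0.162. Adding PS covariates does not alter this formula, so no corrected sample size follows.

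**4. Illustration of the bias.** The documents give neither a prevalence nor a rate ratio, so all inputs here are assumptions. For a binary marker with prevalence pE (empagliflozin) and pC (SU) after matching, and outcome rate ratio RR:

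B = [1 + pE(RR − 1)] / [1 + pC(RR − 1)]

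With pE = 0.30 and pC = 0.40:

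- RR 1.5: B = 1.15/1.20 = 0.958, and 1.5 × 0.958 = 1.44
- RR 2: B = 1.30/1.40 = 0.929, and 1.5 × 0.929 = 1.39

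The chance of wrongly excluding 1.5 when it is true is Φ(−ln B/0.162 − 1.645). It is 5% without bias, about 8% at B = 0.958 and about 12% at B = 0.929.

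A wider set of assumptions, pE = 0.25, pC = 0.30 to 0.45 and RR = 1.25 to 2, gives:

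- B from 1.0625/1.075 = 0.988 down to 1.25/1.45 = 0.862
- a true 1.5 read as 1.48 down to 1.29
- a false-exclusion chance of 5.8% up to 23%

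**5. What cannot be computed.** The share of such a bias that utilization counts would remove depends on how well they track socioeconomic status in these cohorts. The documents give nothing on this.

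**The case against.** Several points on the other side carry weight.

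- **Disclosure.** Section 9.9.2 states the limitation openly. That is to its credit, but disclosure does not adjust for the bias or show whether it survives matching.
- **Existing covariates.** Annex 3 has codes for smoking, alcohol and drug abuse, overweight, obesity, liver disease and hypertriglyceridemia, two comorbidity indexes, a long list of named drugs and 18 drug classes. A reader might infer that the alcohol and smoking pathway is wholly unmeasured. It is not; it is measured incompletely.
- **Fit of the remedy.** Visit and drug counts mainly reflect morbidity and care use, which the indexes and drug classes partly capture. This stands, and it is why the counts can be called only proxies.
- **Insurance type.** A reader might infer that this comes from the same claims in both databases. The documents do not support that: it would come from enrolment data or the source file, and the split is shown for MarketScan only. It probably tracks age, which is already a covariate, and nothing shows that it measures socioeconomic status.
- **Detection.** Sensitivity analysis 1 in protocol 9.7.6 repeats all analyses on the primary discharge diagnosis alone, without the lipase and ultrasound conditions. The tests in the main algorithm fall around an acute presentation, so baseline counts predict them weakly, and Annex 3 already lists baseline ultrasound and lipase. The detection point is therefore secondary and partly covered.
- **Unseen text.** The numbering skips protocol 9.7.5 and SAP 10.5, and the SAP abbreviates high-dimensional propensity score without using it in the visible text. A removed section might bear on unmeasured confounding. This cannot be checked and is not counted as an error. It would not change the visible Annex 3 list.

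**Conclusion.** The point holds in a limited form. The visible candidate list has no baseline health-care-use counts, although the protocol expects socioeconomic channelling, says it will try to include all available confounders, and holds the claims from which the counts can be derived. This is an inexpensive improvement to confounding control, not a defect that invalidates the analysis.

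Two stronger readings are not supported. First, there is no final PS list to fault: section 9.3.3 says only that some covariates will enter, so the gap is in the candidates. Second, the documents do not establish that the result is biased toward excluding 1.5. Section 9.9.2 says background risk may differ, without giving its direction or size. The multipliers of 0.96 to 0.93 (0.988 to 0.862 under the wider inputs) rest wholly on assumed prevalences and rate ratios, and they describe a possible bias, not the benefit of adding the counts.

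**What to change.** Add four variables from the 6-month look-back to SAP Annex 3, the PS model and the standardized-difference table: numbers of hospital admissions, emergency visits, outpatient visits and distinct drugs dispensed. Tabulating them before and after matching would show whether care use differs by more than the plan's 10% threshold.

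Within MarketScan only, the CCAE/MDCR source-file indicator may also be added, with a note that it probably tracks age and is not shown to measure socioeconomic status. If it is used, the SAP should say how it fits with section 9.7.7, which drops from the pooled analysis any variable wholly missing from one database.

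Section 9.9.2 should state that these are proxies and that residual socioeconomic confounding remains possible.

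The cost is a few derived variables, a slightly larger PS model and possibly a few more unmatched patients.
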